- Patients who have been treated with chemotherapy, with biological therapy or other investigational agent must have discontinued the treatment at least 2 weeks (14 days) prior to starting study drug. In case last chemotherapy contains nitrosourea or mitomycin C, the treatment must be discontinued at least 6 weeks prior to the first dose of study drug.
 - Patients, if previously treated with crizotinib must discontinue treatment at least 1 week (7 days) prior to the first dose of study drug.
- 7a. Patient must meet the following laboratory values at the screening visit:
- Absolute Neutrophil Count $\geq 1.5 \times 10^9/L$
 - Platelets $\geq 75 \times 10^9/L$
 - Hemoglobin (Hgb) ≥ 8 g/dL
 - Serum creatinine < 1.5 mg/dL and /or calculated creatinine clearance (using Cockcroft-Gault formula) ≥ 30 mL/min
 - Total bilirubin $\leq 1.5 \times$ ULN except for patients with Gilbert's syndrome who may only be included if total bilirubin $\leq 3.0 \times$ ULN or direct bilirubin $\leq 1.5 \times$ ULN
 - Aspartate transaminase (AST) $\leq 3 \times$ ULN, except for patients with liver metastasis, who are only included if AST $\leq 5 \times$ ULN
 - Alanine transaminase (ALT) $\leq 3 \times$ ULN, except for patients with liver metastasis, who are only included if ALT $\leq 5 \times$ ULN
 - Alkaline phosphatase (ALP) $\leq 5.0 \times$ ULN
 - Serum amylase $\leq 2 \times$ ULN
 - Serum lipase \leq ULN
 - Fasting plasma glucose ≤ 200 mg/dL (≤ 11.1 mmol/L)
8. Patient must have the following laboratory values within normal limits or corrected to within normal limits with supplements during screening:
- Potassium
 - Magnesium
 - Phosphorus
 - Total calcium (corrected for serum albumin)
9. Patient has life expectancy ≥ 6 weeks.
10. Patient has a WHO performance status 0-2.
11. Patient has the ability to understand and provide signed informed consent.
12. Willingness and ability to comply with scheduled visits, treatment plans, laboratory tests and other study procedures.

Patients in Arm 1 to 4 must also meet the following inclusion criteria:

13. Patients must have active brain metastases from NSCLC, confirmed by Gadolinium-enhanced MRI without concomitant leptomeningeal carcinomatosis. Dose of steroids must be stable for 5 days before the baseline brain MRI.

Note: An active brain lesion is a lesion free of any local treatment (like stereotactic radiosurgery or whole brain radiation). The following lesions are considered active:

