Grade 4 (PLT < $25 \times 10^9/L$)	Mandatory: Omit dose until resolved to \leq Grade 2, then \downarrow 1 dose level
HEPATIC	
Alkaline phosphatase and/or Gamma-glutamyl transpeptidase (GGT)	
Isolated elevations of any grade	Recommendation: Maintain dose level
Total Bilirubin** (for patients with Gilbert Syndrome these dose modifications apply to changes in direct [conjugated] bilirubin only)	
Grade 1 ($> ULN$ and $\leq 1.5 \times ULN$)	Recommendation: Maintain dose level with liver function test (LFTs)*** monitored as per protocol
Grade 2 (> 1.5 and $\leq 3.0 \times ULN$) with ALT or AST $\leq 3.0 \times ULN$	Mandatory: Omit dose until resolved to \leq Grade 1, then it is recommended: If resolved in ≤ 7 days, to maintain dose level If resolved in > 7 days, to \downarrow 1 dose level

[figure not shown]
Worst toxicity (CTCAE 4.03 Grade)*	Dose Modifications for ceritinib
Grade 3 (> 3.0 and ≤ 10.0 x ULN) with ALT or AST ≤ 3.0 x ULN	Mandatory: Omit dose until resolved to ≤ Grade 1, then it is recommended: If resolved in ≤ 7 days, to ↓ 1 dose level If resolved in > 7 days, to discontinue patient from ceritinib
Grade 4 (> 10.0 x ULN)	Mandatory: Permanently discontinue patient from ceritinib
AST or ALT	
Grade 1 (> ULN and ≤ 3.0 x ULN)	Recommendation: Maintain dose level with LFTs*** monitored per protocol
Grade 2 (> 3.0 and ≤ 5.0 x ULN) without total bilirubin elevation to > 2.0 x ULN	Recommendation: Maintain dose level with LFTs*** monitored per protocol
Grade 3 (> 5.0 and ≤ 20.0 x ULN) without total bilirubin elevation to > 2.0 x ULN	Mandatory: Omit dose until resolved to ≤ Grade 1, then ↓ 1 dose level
Grade 4 (> 20.0 x ULN) without total bilirubin elevation to > 2.0 x ULN	Mandatory: Omit dose until resolved to ≤ Grade 1, then ↓ 1 dose level
AST or ALT and concurrent Total bilirubin	
AST or ALT > 3.0 x ULN with total bilirubin > 2.0 x ULN in the absence of cholestasis or hemolysis	Mandatory: Permanently discontinue patient from ceritinib Refer to Section 6.3.4.2 for additional follow-up
RENAL	
Serum creatinine	
Grade 1 (>1 and ≤1.5 x baseline; >ULN and ≤ 1.5 x ULN)	Recommendation: Maintain dose level
Grade 2 (> 1.5 and ≤ 3 x baseline; >1.5 and ≤3.0 x ULN)	Recommendation: Omit dose until resolved to ≤ Grade 1, then it is recommended: If resolved in ≤ 7 days, then maintain dose level If resolved in > 7 days, then ↓ 1 dose level
Grade 3 (>3.0 x baseline; > 3.0 and ≤ 6.0 x ULN)	Mandatory: Omit dose until resolved to ≤ Grade 1, then ↓ 1 dose level

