6.3.4.1 Guidelines for the follow-up of laboratory hematologic abnormalities

In case of any occurrence of febrile neutropenia, neutropenia \geq grade 3 or thrombocytopenia \geq grade 3, tests must be performed weekly (or more frequently if clinically indicated) until the event resolves to \leq grade 2. Subsequent monitoring must be performed every 4 weeks. See [Table 6-4](#).

6.3.4.2 Guidelines for the follow-up of laboratory liver abnormalities and potential drug-induced liver injury (DILI) cases

In patients with any clinically relevant laboratory liver abnormality, as defined below, hepatic toxicity monitoring must include ALL of the following liver function tests (LFTs): albumin, ALT, AST, total bilirubin (fractionated if total bilirubin $>$ 2.0 x ULN), alkaline phosphatase and GGT. Note: for patients with Gilbert Syndrome, total and direct bilirubin must be monitored, but intensified monitoring applies to changes in direct bilirubin only.

[figure not shown]
In case of any occurrence of ALT/AST/total bilirubin increase to grade 2 the LFTs must be monitored weekly (or more frequently if clinically indicated) until the event resolves to \leq grade 1. Thereafter monitoring must be continued every other week (or more frequently if clinically indicated) for two additional cycles (e.g. 8 weeks). If there is no recurrence of grade 2 ALT/AST/total bilirubin elevations during this period, subsequent monitoring must be performed every 4 weeks. For patients with liver metastasis and grade 2 AST/ALT at baseline, increased monitoring is required for grade 3/4 AST/ALT; follow guidelines for grade 3 or 4 AST/ALT.

In case of any occurrence of ALT/AST/total bilirubin increase to grade 3 or 4, LFTs must be monitored weekly (or more frequently if clinically indicated) until the event resolves to \leq grade 1. Thereafter monitoring must be continued every other week (or more frequently if clinically indicated) for four additional cycles (e.g. 16 weeks). If there is no recurrence of \geq grade 2 ALT/AST/total bilirubin elevations during this period, subsequent monitoring must be performed every 4 weeks.

Patients who discontinue study treatment due to liver toxicity must be monitored weekly (or more frequently if clinically indicated) until the event resolves to \leq grade 1 or stabilization occurs (no CTCAE grade change over 4 weeks). Refer to [Table 6-4](#).

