7.2.2.6 Laboratory evaluations

Central laboratories will be used for the analysis of scheduled hematology, biochemistry and other blood specimens collected as part of safety monitoring (as detailed in [Table 7-1](#)). Dipstick urinalysis will be performed locally (unless local institution policies dictate otherwise), except in the case of any out of range parameter on scheduled local urinalysis, when a urine sample will be sent to central laboratory for further analysis. Laboratory values obtained during the Screening phase will be used to assess patient's eligibility. The time windows granted for laboratory evaluations are identical to the corresponding visit time windows for each visit (refer to [Section 7.1](#)).

The site does not need to wait for the results of centrally-analyzed laboratory assessments when an immediate clinical decision needs to be made and in those cases locally unscheduled testing may be performed.

Details on the collection, shipment of samples and reporting of results by the central laboratory are provided to investigators separately.

Table 7-4 Clinical laboratory parameters collection plan

Test Category	Test Name
Hematology	Hemoglobin, Platelets, White blood cells (WBC) with Differential (Basophils, Eosinophils, Lymphocytes, Monocytes, Neutrophils in percentage or absolute)
Chemistry	Albumin, ALT, AST, calcium (at screening calcium corrected for albumin will be tested in addition to calcium), creatinine, creatinine clearance, total bilirubin, direct bilirubin (only if total bilirubin is \geq grade 2), blood urea nitrogen (BUN) or urea, magnesium, potassium, sodium, fasting glucose, phosphate (inorganic phosphorus), alkaline phosphatase, amylase, lipase, GGT
Urinalysis	Macroscopic Panel (Dipstick) (Color, bilirubin, Blood, Glucose, Ketones, Leukocyte esterase, nitrite, pH, protein, specific gravity, urobilinogen) Microscopic panel (RBC, WBC, casts, crystals, bacteria, epithelial cells)
Pregnancy	At screening visit, serum pregnancy test At subsequent cycles, urinary pregnancy test. If local requirements dictate otherwise, local regulations should be followed
Coagulation	Pro-thrombin time (PT) and International normalized ratio [INR] or Quick Test

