7.2.2.6.2 Clinical chemistry

Blood chemistry assessments of the parameters listed in [Table 7-4](#) will be tested as per the schedule of assessments ([Table 7-1](#)).

[figure not shown]

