### **Laboratory data**

For laboratory data assessments, data from all sources (central and local laboratories) will be combined. The summaries will include all laboratory assessments collected in the on-treatment period. All laboratory assessments will be listed and those collected prior to first dose of study drug or later than 30 days after study drug discontinuation will be flagged in the listings.

Laboratory data will be classified (by Novartis Oncology Statistical Programming) into CTC grades according to the NCI CTCAE v4.03. For all reports, CTC grade is always obtained on the converted measurement in SI unit. Grade 5 will not be used. The CTC grade 0 will be assigned as below in different scenarios:

1. For laboratory parameters defined by criteria based on normal range only, a severity grade of 0 will be assigned when the value is within normal limits.
2. For laboratory, parameters whose grade is defined by criteria based on normal range and absolute values (e.g. platelet count decrease). A severity grade of 0 will be assigned when the value is within normal limits.
3. For laboratory parameters whose grade is defined by criteria based on normal range and the change from baseline value, with no other associated clinical criteria such as concomitant medication (e.g. creatinine increased) the following will be applied. For the baseline grading and for the grading of post-baseline laboratory values with missing baseline grading, the grade will be derived using the criteria based only on the normal range as per CTCAE v4.03. A severity grade of 0 will be assigned when the post-baseline value is  $\leq$  ULN (for hyper) or  $\geq$  LLN (for hypo).

Parameters for which a grading does not exist will be classified into low/normal/high group by means of laboratory normal ranges.

The following summaries will be produced for the hematology and biochemistry laboratory data (by laboratory parameter):

- Shift tables using CTC grades to compare baseline to the worst post-baseline value for laboratory parameters with CTC grades
- Shift tables using low, normal, high (as well as low and high combined) classifications to compare baseline to the worst post-baseline value for laboratory parameters where CTC grades are not defined.

The following lab parameters will be summarized:

- Hematology: absolute lymphocytes, absolute neutrophils, hemoglobin (anemia), WBC, platelet counts, absolute basophils, absolute eosinophils, absolute monocytes, RBC.

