- Biochemistry: alkaline phosphatase (ALP), SGPT (ALT), SGOT (AST), total bilirubin, amylase, lipase, potassium (hyper and hypo), sodium (hyper and hypo), creatinine, glucose (hyper and hypo), phosphate, albumin, calcium (corrected for albumin), magnesium, creatinine clearance, direct bilirubin, blood urea nitrogen (BUN) or urea, GGT.
- For bi-directional parameters, both hyper and hypo summaries will be presented.

All hematology and biochemistry will be listed as per protocol. Further, following laboratory parameters will be presented in listings and will not be summarized:

- Coagulation: INR, pro-thrombin time (PT) or Quick Test.

Other laboratory parameters collected and not described above may be summarized if clinically indicated.

The following listings will be produced for the laboratory data for all laboratory parameters where CTC grades are defined:

- Listing of patients with laboratory abnormalities of CTC grade 3 or 4.
- Listing of all laboratory data with values flagged to show the corresponding CTC grades and the classifications relative to the laboratory reference ranges.

Liver function tests (LFTs) of interest for ceritinib are total bilirubin (TBILI), ALT, AST and ALP. In what follows, AT refers to ALT or AST values. LFTs will be summarized as follows:

- Shift tables of baseline vs. worst post-baseline on-treatment values for the categories:
  - $TBILI \leq 2xULN$ ,  $TBILI > 2xULN$  and missing TBILI
  - $ALT \leq 3xULN$ ,  $ALT > 3xULN$  and missing ALT
  - $AST \leq 3xULN$ ,  $AST > 3xULN$  and missing AST
  - $ALP < 2xULN$ ,  $ALP \geq 2xULN$  and missing ALP
- Frequency counts and percentages of patients with worst post-baseline on-treatment values in the categories:
  - $ALT > 3xULN$ ,  $ALT > 5xULN$ ,  $ALT > 10xULN$ ,  $ALT > 20xULN$
  - $AST > 3xULN$ ,  $AST > 5xULN$ ,  $AST > 10xULN$ ,  $AST > 20xULN$
  - $AT > 3xULN$ ,  $AT > 5xULN$ ,  $AT > 10xULN$ ,  $AT > 20xULN$
  - $TBILI > 2xULN$
  - Concurrent  $ALT > 3xULN$  and  $TBILI > 2xULN$
  - Concurrent  $AST > 3xULN$  and  $TBILI > 2xULN$
  - Concurrent  $AT > 3xULN$  and  $TBILI > 2xULN$
  - Concurrent  $AT > 3xULN$  and  $TBILI > 2xULN$  and  $ALP < 2xULN$
  - Concurrent  $AT > 3xULN$  and  $TBILI > 2xULN$  and  $ALP \geq 2xULN$

Concurrent measurements are those occurring on the same date.

In addition, a listing of all TBILI, ALT, AST and ALP values for patients with a post-baseline  $TBILI > 2xULN$ ,  $ALT > 3xULN$  or  $AST > 3xULN$  will be provided.

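### Direct bilirubin is scheduled only once total bilirubin reaches grade 2, yet the Gilbert's dose rules and a SAP shift table rely on it, so the baseline will be mostly missing and a rule-relevant value may go unmeasured

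*Protocol*

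**What the plan says.** - **Protocol 7.2.2.6, Table 7-4 (chemistry row):** "direct bilirubin (only if total bilirubin is" grade 2 or higher. Section 7.2.2.6.2 ties the scheduled panel to this table: "Blood chemistry assessments of the parameters listed in" Table 7-4 follow the visit schedule. No exception is written for Gilbert's syndrome or for baseline.
- **Protocol Table 6-3 (hepatic, total bilirubin):** the second grade begins above 1.5 x ULN ("Grade 2 (> 1.5 and" at most 3.0 x ULN). The row heading adds: "for patients with Gilbert Syndrome these dose modifications apply to changes in direct [conjugated] bilirubin only". No condition on the total is attached.
- **Protocol 6.3.4.2:** "for patients with Gilbert Syndrome, total and direct bilirubin must be monitored". Intensified monitoring in these patients also follows direct bilirubin only.
- **Protocol 5.2, criterion 7a:** total bilirubin must be at or below 1.5 x ULN, "except for patients with Gilbert's syndrome who may only be included if" the total is no more than 3.0 x ULN or the direct value no more than 1.5 x ULN.
- **SAP 2.8.2, Laboratory data:** the biochemistry parameters to be summarised include "creatinine clearance, direct bilirubin, blood urea nitrogen (BUN) or urea, GGT". Graded parameters get a shift table by CTC grade. Ungraded ones get "Shift tables using low, normal, high (as well as low and high combined) classifications to compare baseline to the worst post-baseline value". Either way, each patient needs a baseline value.

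**The concern.** Two uses of direct bilirubin do not match the rule for collecting it.

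The first is clinical. For Gilbert's patients the dose actions depend on direct bilirubin, but the laboratory plan runs the assay only after total bilirubin has crossed a threshold. The dose rule also refers to changes, and a change cannot be judged without an earlier value.

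The second is statistical. A shift table cross-classifies baseline against worst later value. If the baseline is unscheduled for most patients, and later values arise mainly once the total is already high, the table reflects who was sampled more than what the drug did.

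**Working it through.** The plan states no figure to reproduce. The check sets the passages against each other, with one piece of algebra.

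**1. Who has a scheduled baseline direct value?** Cross criterion 7a with the Table 7-4 trigger (total above 1.5 x ULN):

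| Patient at screening | Total bilirubin | Direct scheduled? |
|---|---|---|
| Non-Gilbert's, eligible | at or below 1.5 x ULN (grade 0-1) | No |
| Gilbert's | at or below 1.5 x ULN | No |
| Gilbert's | above 1.5 x ULN | Yes |

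Other sources are limited. A total may rise to grade 2 by Day 1, or a test may be done off schedule. The SAP baseline is the last available assessment on or before the start of treatment, unscheduled assessments count, and central and local results are pooled. Such values would be incidental.

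**2. Who has a post-baseline value?** By schedule, only patients whose total is at that moment grade 2 or higher. Section 6.3.4.2 adds Gilbert's patients under follow-up for a liver abnormality. Post-baseline values are therefore largely selected on a raised total.

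**3. Can a dose trigger be missed in a Gilbert's patient?** Grade 1 calls for no dose change, so the question is whether direct bilirubin can pass 1.5 x its reference limit while the total is at or below 1.5 x ULN. Let T = t x ULN(total) with t ≤ 1.5, let the direct value be D = f x T with f ≤ 1, and let r = ULN(direct)/ULN(total).

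The trigger is D > 1.5 x ULN(direct), that is, f x t > 1.5 x r, so f > 1.5r/t. At the boundary t = 1.5 this becomes f > r.

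- If the total-bilirubin ULN is used for both (r = 1), f would have to exceed 1, which is impossible. Table 7-4 then always measures direct bilirubin when a grade 2 action is due.
- If direct bilirubin has its own lower ULN (r < 1), a trigger is possible without a measurement. At the boundary, r = 0.5 needs a direct fraction above 50% and r = 0.2 needs one above 20%. These values of r are assumptions; the documents give none.

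Criterion 7a sets separate limits for total and direct bilirubin, which reads more naturally as two ULNs, but no passage says so.

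**The case against.** The strongest reply is that the gap may never open. The Table 6-3 bands are headed as total bilirubin and name one ULN; if it serves both analytes, no grade 2 trigger is missed. Section 6.3.4.2 already requires direct bilirubin in Gilbert's patients during liver follow-up, Section 7.2.2.6 permits local testing when a decision cannot wait, and detailed laboratory instructions are given to sites separately. All of this stands, and it makes the missed trigger conditional. It does not remove the conflict: Section 6.3.4.2 is framed around patients who already have a liver abnormality, Table 7-4 carries no matching exception, and the ULN is not stated.

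Four stronger readings are tempting, and the documents do not support them.

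- **The baseline column will be empty.** Gilbert's patients entering above 1.5 x ULN have a scheduled value, anyone admitted on the direct-bilirubin limb of criterion 7a must have been measured, and unscheduled or local results count.
- **The trigger cannot be seen.** This holds only if r < 1 and the direct fraction is high enough, and neither is documented.
- **Fractionating above 2.0 x ULN in Section 6.3.4.2 contradicts the 1.5 x ULN trigger.** Any total above 2.0 x ULN is already grade 2 or higher, so following Table 7-4 at scheduled chemistry satisfies both.
- **The hepatotoxicity analysis is compromised.** Adverse events of special interest are found by preferred term, and the SAP's liver tests of interest are total bilirubin, ALT, AST and ALP.

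**Conclusion.** The point holds in limited form. The collection rule for direct bilirubin does not agree with the Gilbert's rules that depend on it. Whether a dose-relevant value would actually be missed depends on the unstated ULN. Apart from that, a Gilbert's patient entering with total at or below 1.5 x ULN has no scheduled baseline from which to judge a change.

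The SAP part needs no assumption about the ULN. For eligible non-Gilbert's patients the plan schedules no screening value, so the shift table will have a mostly missing baseline and selectively sampled follow-up. The SAP names a missing category for its four liver tests of interest but none for direct bilirubin.

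No numerical size can be given: the number of Gilbert's patients, the reference limits and the direct fractions are not in the documents. This is a small correction to safety monitoring and reporting.

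**What to change.** **Protocol.** The sponsor should reconcile Table 7-4, the Gilbert's note in Table 6-3 and Section 6.3.4.2 so that the collection plan and the rules that use direct bilirubin agree, and should state which ULN applies to it. Which threshold or schedule is right is a clinical matter; none is proposed here. Enrolment closed in August 2017, so this serves patients still on treatment and the interpretation of the data.

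**SAP 2.8.2.** Take direct bilirubin out of the shift tables and list it. Alternatively, keep a shift summary limited to patients with both a baseline and a post-baseline value, show the number missing, and note that collection was triggered by total bilirubin.

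**Cost.** One line in the SAP, made before database lock, and wording in three protocol places. The only loss is a less complete descriptive table for one analyte.

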7.2.2.6.1 Hematology

Hematology assessments of the parameters listed in [Table 7-4](#) will be tested as per the schedule of assessments ([Table 7-1](#)).

7.2.2.6.2 Clinical chemistry

Blood chemistry assessments of the parameters listed in [Table 7-4](#) will be tested as per the schedule of assessments ([Table 7-1](#)).

[figure not shown]
7.2.2.6.3 Urinalysis

Dipstick measurements will be performed as per [Table 7-4](#) and according to the schedule of assessments. Any significant findings on dipstick will be followed up with microscopic evaluation as per [Table 7-4](#). In the event this is not allowed per institution or local clinical practice, site must ensure completion, as well as record of rationale for use and results of local lab analysis are available in source documentation and clinical database.

7.2.2.6.4 Pregnancy and assessments of fertility

During screening, a serum pregnancy test will be completed (Day -28 to Day -1). On Cycle 1 Day 1 prior to dosing and at subsequent cycles and at EOT, urinary pregnancy test (dipstick) will be performed. The time windows granted for pregnancy testing are identical to the corresponding visit time windows for each visit. Refer to [Table 7-1](#). If local requirements dictate otherwise, local regulations should be followed.

Women who are determined not to be of child bearing potential before the study will only be tested at screening. When non-child bearing potential status is determined during the study, further pregnancy testing will not be continued. Women are considered post-menopausal if they have had 12 months of natural (spontaneous) amenorrhea with an appropriate clinical profile (e.g. age appropriate, history of vasomotor symptoms), and otherwise not of child bearing potential if they have had surgical bilateral oophorectomy (with or without hysterectomy) or tubal ligation at least six weeks ago. In the case of oophorectomy alone, only when the reproductive status of the woman has been confirmed by follow up hormone

level assessment is she considered not of child bearing potential (such testing is not covered as part of the study assessments). If local requirements dictate otherwise, local regulations should be followed.

The time windows granted for pregnancy testing are identical to the corresponding visit time windows for each visit. Refer to [Table 7-1](#).

If a positive pregnancy test is performed in between study visits, the patient must immediately notify the investigator.

Male patients must notify the investigator in case their partner is confirmed with positive pregnancy test results during the treatment period.

